### **5.2.2 Selection and Timing of Dose for Each Subject**

The study drug (teduglutide 0.05 mg/kg/day) will be self-administered immediately after reconstitution by SC injection into 1 of the 4 quadrants of the abdomen or into either thigh or arm. Subjects will be trained to self-inject teduglutide on Day 0. The first SC injection should be administered under the supervision of the investigator or designee and the subject observed for at least 4 hours. Detailed instructions for reconstitution and injection of the study drug can be found in the Injection Instruction Leaflets and the study reference manual. Each day, the injection site should be changed. Subjects with a stoma must avoid using the abdominal quadrant in which the stoma is situated.

The subject should be dosed at approximately the same time each day. If a subject forgets to take drug, that day's dose should be administered as soon as possible, even if this is later in the day or evening. Consecutive doses should be separated by approximately 12 hours.

Dosing must be performed at least 14 hours prior to antibody testing, which will be performed at baseline and at Weeks 12 and 24 during Period 2 and at Months 6, 12, and 24 during Period 3.

The investigator is responsible for contacting the sponsor or designee prior to interrupting or modifying the subject's daily study drug dosing regimen, ie, as consideration for tolerability issues.

A single discontinuation period of study drug should not exceed 10 consecutive days. Dosage interruptions of study drug are permissible for a maximum of 21 days total per each 24-week period throughout the study.

Dates of days with missed or incomplete doses are to be reported in the diary.

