**Test product, dose and mode of administration:** Teduglutide for subcutaneous (SC) injection is provided as a lyophilized powder that must be reconstituted using 0.5 mL sterile water for injection and used within 5 minutes of reconstitution.

A daily dose of teduglutide 0.05 mg/kg will be used in this study. The dose calculation will be based on an average of the 2 measurements of body weight at the stabilization and baseline visits. This calculated dose will be used for the duration of the study.

Teduglutide will be administered by SC injection once daily into 1 of the 4 quadrants of the abdomen or either thigh or arm. The first SC injection should be administered under the supervision of the investigator or designee.

**Reference therapy, dose and mode of administration:** This is an open-label study.

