## 1 INTRODUCTION

### 1.1 Background

#### Compound

Teduglutide is a novel, recombinant analog of naturally occurring human glucagon-like peptide (GLP)-2 that regulates the functional and structural integrity of the cells lining the gastrointestinal (GI) tract. Teduglutide is a 33-amino acid peptide that differs from native GLP-2 in the substitution of glycine for alanine at the second position at the N-terminus. As a result, teduglutide demonstrates resistance to degradation by dipeptidyl peptidase 4 and therefore maintains a longer elimination half-life of approximately 2 hours compared to the native peptide, which has a  $t_{1/2}$  of approximately 7 minutes. Teduglutide has been shown in animal studies and previous human clinical trials to increase villus height and crypt depth in the intestinal epithelium, thereby increasing the absorptive surface area of the intestines. The European Commission granted a centralised marketing authorization valid throughout the European Union for teduglutide (Revestive®) on 30 August 2012 and a New Drug Application for teduglutide (Gattex®) was approved by the US Food and Drug Administration on 21 December 2012 for the treatment of adult patients with short bowel syndrome (SBS) who are dependent on parenteral support.

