## **5.1 Treatments Administered**

Teduglutide 0.05 mg/kg/day will be administered daily at home by the subjects, who will self-administer the study drug by SC injection into either thigh or arm or one of the 4 quadrants of the abdomen.

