### **5.1.3 Storage, Accountability, and Stability**

Study drug will not be dispatched to the center until the sponsor or designee has received all required documents from the study center in accordance with applicable regulatory requirements and relevant standard operating procedures.

The investigator or designee will conduct an inventory upon receipt of the clinical supplies and will acknowledge receipt of the supplies to the sponsor or designee. A copy of the shipping documents must be maintained for the investigator's records. Study drug must be kept in a locked area with access restricted to specific study personnel. Study drug must be stored refrigerated at a temperature between 2 and 8°C (36 to 46°F) until dispensed. Once dispensed to a subject, the study drug and the sterile water diluent should be kept at 15 to 25° C (59 to 77°F). If there are concerns that this temperature cannot be maintained, the study drug may be refrigerated. Therefore, the overall acceptable storage temperature range is 2 to 25°C (36 to 77°F).

Study drug kits will be dispensed to subjects at each of the study visits. Each study drug kit is sufficient for a treatment period of 1 week and enough kits are to be supplied to cover the period until the next planned study visit. Additional study kits will be provided as necessary.

The investigator is to keep a current record of the inventory and dispensing of all clinical supplies. This record will be made available to the sponsor's monitor for the purpose of accounting for all clinical supplies. Any discrepancy or deficiency will be recorded, with an explanation. All supplies sent to the investigator must be accounted for and in no case will clinical supplies be used in any unauthorized situation.

All used and unused study drug vials, including the supplies must be returned by the subjects and retained at the center until instructions are received for return and/or destruction of supplies. Further details will be provided in the study reference manual.

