## Overdose

Defined as an accidental or intentional administration of an excessive dose of a product, an overdose should be reported to the sponsor using the SAE form. This information will be shared with the NPS Safety Management Team (SMT) and the sponsor's medical monitor.

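### Section 5.2.2 sets about 12 hours between consecutive doses, which contradicts once-daily dosing at the same time each day (about 24 hours); a minimum gap after a late dose was probably meant.

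*Protocol*

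**What the plan says.** The dosing regimen appears in several places. The Summary, under the test product, states: "Teduglutide will be administered by SC injection once daily into 1 of the 4 quadrants of the abdomen", with either thigh or arm as alternatives. Section 5.1 states: "Teduglutide 0.05 mg/kg/day will be administered daily at home by the subjects".

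Section 5.2.2 then has a three-sentence paragraph on timing:

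- The first sentence fixes the clock time: "The subject should be dosed at approximately the same time each day".
- The second covers a forgotten dose. That day's "dose should be administered as soon as possible, even if this is later in the day or evening".
- The third reads: "Consecutive doses should be separated by approximately 12 hours".

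The third sentence is identical in all three complete protocol versions in the file. A further version, apparently the newest, is shown only in part. Its Summary still specifies once-daily injection, but the text stops before its Section 5.2.2.

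**The concern.** A spacing rule for consecutive doses should give the interval that the regimen implies, or else be marked as a lower limit for a particular situation. This sentence does neither. It gives a target interval that is half the one implied by the regimen, and it applies on its face to every pair of doses.

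The instruction matters because dosing is unsupervised after the first injection and lasts 24 weeks, then up to 24 further months. Late doses will happen over that time, and this paragraph is where the protocol says what to do about them. If someone followed the sentence literally and took an extra dose, the daily dose would be exceeded. The protocol counts an excessive dose as an overdose, and "an overdose should be reported to the sponsor using the SAE form". An avoidable wording error could therefore create a reportable event.

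**Working it through.** **Inputs**

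- Dosing frequency: once daily (Summary, test product; Section 5.1).
- Daily dose: 0.05 mg/kg (Sections 5.1 and 5.2.2).
- Stated spacing: about 12 hours (Section 5.2.2).
- Half-life: Section 1.1 says that teduglutide "maintains a longer elimination half-life of approximately 2 hours".
- Antibody sampling: before the day's dose and at least 14 hours after the previous one (Section 6.2).

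**1. Interval implied by the regimen**

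Interval = 24 h / doses per day = 24 / 1 = 24 h. The stated 12 h cannot be reproduced from the regimen.

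**2. Regimen implied by the stated interval**

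Doses per day = 24 / 12 = 2. Daily dose = 2 × 0.05 = 0.10 mg/kg, twice the specified dose. A regular 12-hour interval would also make the antibody sampling rule impossible to meet, since 14 h > 12 h. The literal reading therefore conflicts with three other instructions: once-daily frequency, a fixed clock time, and the sampling gap.

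**3. The sentence read as a target after a late dose**

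If a dose is L hours late and the next is taken at the usual time, the gap is 24 − L hours.

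| L (hours late) | Gap to the usual time (h) | Agrees with a target of about 12 h? |
|---|---|---|
| 4 | 20 | No |
| 12 | 12 | Yes |
| 14 | 10 | Short by 2 h |

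As a target, 12 hours agrees with the fixed clock time only when the dose is about 12 hours late, for example a morning dose taken that evening. For a dose 4 hours late, it would bring the next dose forward by 20 − 12 = 8 hours from the usual time.

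**4. The sentence read as a minimum after a late dose**

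A floor of 12 hours matters only if 24 − L < 12, that is, if L > 12. For any dose up to 12 hours late, the subject simply returns to the usual time. For L = 14, the next dose waits 14 − 12 = 2 hours past the usual time, and the following one is 24 − 2 = 22 hours later, back on schedule. This reading fits the rest of the paragraph, but it needs the words *at least* and *after a late dose*, and neither is there.

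**5. Carry-over**

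Assuming simple exponential decline with a 2-hour half-life, the fraction remaining is 0.5^(12/2) = 0.0156, about 1.6%, at 12 h, and 0.5^(24/2) = 0.00024, about 0.02%, at 24 h. One shortened gap leaves very little drug from the previous dose.

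**The case against.** The strongest reply is that the sentence works in its paragraph. It comes directly after the forgotten-dose rule. If a morning dose is taken that evening, the next morning's dose follows about 12 hours later, which is the case the paragraph has in mind. On that reading there is no conflict with once-daily dosing, and the point is a copy-edit.

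Much of this stands. The context makes the intended meaning fairly clear, and it is too strong to say that a late-dosing subject has no guidance: the contextual reading says to leave about 12 hours. What does not stand is that context cures the rule. The restriction to late doses is inferred, and even with it a 12-hour target gives the wrong answer for a dose only a few hours late.

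A reader might also infer from the literal text that subjects would inject twice a day. The documents do not support that. The daily dose is stated repeatedly, the forgotten-dose rule speaks of a single day's dose, the investigator must contact the sponsor before the regimen is modified, and supply is limited: "Each study drug kit is sufficient for a treatment period of 1 week". Section 5.2.4 adds vial counts and a compliance question at every visit. Sustained doubling would be hard to reach and quickly seen; at most an isolated extra dose is conceivable.

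Nor can it be assumed that subjects ever see this sentence. They are trained on Day 0 and referred to the injection leaflets and the study reference manual, which are not shown.

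**Conclusion.** The sentence is wrong as written: it states about 12 hours where the regimen requires about 24. The severity is low. It is a faulty number in an operative dosing rule, and the once-daily design itself is not in question.

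A reader might go further and infer an effect on exposure or results. There is no support for that. Planned exposure stays at 0.05 mg/kg/day, no efficacy endpoint depends on the sentence, and the pharmacokinetic parameters come from a single-dose profile planned for the first day of treatment. Nor can it be said that the error persists in the newest version, because its Section 5.2.2 is not available.

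The conclusion that the text is wrong rests on the wording alone. Three things are assumptions: that a minimum gap after a late dose was intended (inferred from position), that the partly shown version is the newest, and that decline is simple exponential (used only for the carry-over figures).

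**What to change.** Replace the sentence in Section 5.2.2 with:

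*Doses are taken once daily at about the same time (about 24 hours apart). After a late dose, take the next dose at the usual time, provided at least 12 hours have passed; otherwise wait until 12 hours have passed.*

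This keeps the 12-hour figure as a floor, confines it to late doses, and says explicitly when to return to the usual time. The antibody sampling rule needs no added text, because Section 6.2 already sets the 14-hour gap.

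Check the injection leaflet, the study reference manual and Section 5.2.2 of the newest version for the same wording, and correct them together.

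The cost is a short text replacement in the next amendment plus that check. Visits, sample size and analysis are unchanged.

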### **5.2.3 Subjects Who Achieve PN/I.V. Independence**

Any subject who achieves complete independence from PN/I.V. support (either during optimization or at any time during the Stage 2 or 3 treatment period) will continue to receive teduglutide treatment. A subject will be considered to have achieved independence from PN/I.V. (completely weaned off PN) if the investigator prescribes no PN and there is no use of PN recorded in the subject diary at the last dosing visit.

If a subject relapses following achievement of PN/I.V. independence, PN/I.V. support will be re-initiated and the subject will continue receiving teduglutide.

## **5.2.4 Compliance with Dosing Regimens**

Subject compliance with study drug dosing will be monitored by the sponsor or designee by counting and examining used and unused vials. In addition, compliance will be checked at every visit by asking the subjects if they have taken their study drug according to instructions and by performing drug accountability.

Compliance is considered to be achieved if the subject has 80% of the planned doses administered.

## **5.3 Prior and Concomitant Medications**

The administration of all medications including concomitant medications (including prescription and nonprescription medications, dietary and nutritional supplements, and vitamins), study drug, and PN/I.V. must be recorded in the appropriate sections of the CRF.

No new medications should be started unless medically necessary and prescribed by the investigator or by another qualified physician involved in the subject's clinical care and who is aware of the subject's study participation.

The mechanism of action of teduglutide may increase absorption of orally administered drugs (eg, motility medication, warfarin, psychotropics, and digoxin), so consideration should be given to modifying concomitant medication regimens. Down-titration of concomitant medication dosages should be considered when drugs, including those with a narrow therapeutic range, are given, especially if given at dosages that are higher than usual.

# **6 STUDY EVALUATIONS AND PROCEDURES**

The objectives of this clinical study are to evaluate the safety, efficacy and pharmacokinetics of teduglutide in Japanese subjects with PN/I.V.-dependent SBS over a 24-week period (Stage 2) followed by a long-term extension (Stage 3) to evaluate safety and continued efficacy.

## **6.1 Efficacy Evaluations**

Reductions in PN/I.V. volume form the basis for most of the efficacy evaluations. The procedures for the stepwise reduction of PN/I.V. during Stages 2 and 3 of this study are given in [Appendix 2](#) and [Appendix 3](#), respectively.

As described in Section [2.1](#), the efficacy endpoints for Stage 2 are as follows:

- Absolute and percent change from baseline in weekly PN/I.V. volume over 24 weeks

- Percentage of subjects who demonstrate a response at Week 20 and again at Week 24.
- Change in days per week of PN/I.V. support
- Changes in plasma citrulline levels from baseline to Week 24 (or EOT)

In Stage 3, absolute and percent change from baseline in weekly PN/I.V. volume and changes in days per week of PN/I.V. support and plasma citrulline levels will continue to be evaluated throughout the long-term extension (see Section 2.2).

Single-dose pharmacokinetics will be evaluated on the first day of teduglutide treatment (Day 0) in Stage 2 only, and pharmacokinetic parameters will be derived as described in Section 2.3.

## 6.2 Safety Evaluations

Safety will be assessed by evaluations of the following variables:

- Adverse events, including GI symptoms
- 12-lead ECGs
- Vital signs, including changes in body weight and BMI
- Laboratory safety data, including electrolyte balance
- Antibodies to teduglutide and ECP. Samples for antibody analysis will be drawn at the start of treatment and at the EOT visit (prior to the administration of teduglutide and at least 14 hours after the previous dose). A 6-month follow-up is planned for any subjects testing positive for teduglutide-specific antibodies following the last dose of study drug.
- Changes in urine output (48-hour oral fluid intake/urine output)
- Abdominal ultrasound
- Upper GI contrast series with small bowel follow-through
- Colonoscopy/sigmoidoscopy of remnant colon
- Physical examinations

### 6.2.1 Adverse Events

During the study, the investigator is responsible for the detection and documentation of any AE or SAE, as defined in this protocol.

### **6.2.1.1 Adverse Event Definition**

An AE is defined as any untoward medical occurrence in a subject or clinical investigation subject administered a pharmaceutical/medicinal product. An AE does not necessarily have to have a causal relationship with this treatment.

An AE can therefore be any unfavorable and unintended sign (including a clinically significant abnormal laboratory finding, for example), symptom, or disease temporally associated with the use of a medicinal product (investigational or marketed), whether or not considered related to treatment with the medicinal product.

An AE includes:

- An exacerbation of a pre-existing illness, sign, symptom, or clinically significant (as determined by the investigator) laboratory test abnormality and clinically significant ECG abnormality
- An illness, sign, symptom, or clinically significant laboratory abnormality that is detected or diagnosed after study drug administration
- Pretreatment or post-treatment events that occur as a result of protocol-mandated procedures

An AE does not include:

- The disease or disorder being studied or signs and symptoms associated with the disease or disorder, unless there is worsening of the condition of the disease or disorder
- A pre-existing disease or condition, present at the start of the study, that does not worsen

## Overdose

Defined as an accidental or intentional administration of an excessive dose of a product, an overdose should be reported to the sponsor using the SAE form. This information will be shared with the NPS Safety Management Team (SMT) and the sponsor's medical monitor.

### 6.2.1.2 Procedures for Reporting Adverse Events

Adverse events may be spontaneously reported by the subject, obtained through nonleading questioning, or noted during examination of a subject. Adverse events will be recorded from the signing of the ICF through the last dose of study drug. Adverse events that are not resolved at the end of study will be monitored with a telephone call by the investigator, as necessary, for approximately 4 weeks after the last dose of study drug or until resolution or until the AE is judged by the investigator to have stabilized.

As they occur, new AEs will be recorded sequentially on the AE page of the CRF. The AE term should note the diagnosis whenever possible, not the individual signs or symptoms (eg, myocardial infarction should be recorded rather than chest pain, elevated cardiac enzymes, and abnormal ECG). Also recorded are:

- Start and stop date and time (date the site becomes aware of the SAE)
- Whether the event is continuing
- Frequency (intermittent, continuous)
- Intensity (mild, moderate, severe)
  - Mild: usually transient, requiring no special treatment and generally not interfering with usual daily activities
  - Moderate: usually ameliorated by simple therapeutic maneuvers and impairs usual activities
  - Severe: requires vigorous therapeutic intervention and interrupts usual activities. Hospitalization may or may not be required.
- Relationship to study drug (not related, related): identify relationship as "related" if a causal relationship between the investigational product and an AE is at least a reasonable possibility
- Whether the AE is serious (ie, an SAE). If identified as an SAE, the AE should be reported on the SAE form according to Section [6.2.2](#) below
- Actions taken (none; study drug dose changed, interrupted, or discontinued; other medication change; nondrug therapy)
- Outcome (resolved, resolved with sequelae, ongoing, fatal). An individual AE receives only one outcome.

Adverse events that are related to study drug and not resolved at the end of treatment will be followed by the site until resolution or until the AE is judged by the investigator to have stabilized.

Laboratory values, blood pressure, ECG evaluations, and clinical findings at the scheduled physical examinations must be reported as AEs if they:

- Are considered clinically significant by the investigator (ie, not part of the subject's medical history),
- Fulfill SAE criteria, and/or
- Cause subject discontinuation from the study.

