## **6.2.2      Serious Adverse Events**

An SAE must be recorded on the SAE Form. An SAE requires expeditious handling to comply with regulatory requirements. Any SAEs occurring from the signing of the ICF through 30 days after the last dose of study drug will be captured and must be reported within 24 hours after the investigator is made aware of the event.

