### **Antibodies to teduglutide and ECP**

Blood samples for analyses of antibodies to teduglutide and to ECP will be collected at baseline and at Weeks 12 and 24 or early termination during Stage 2 of the study, and at Months 6 and 12, and at the final visit or early termination in Stage 3.

If teduglutide-specific antibodies are detected, subjects may remain in study and will continue to be tested at each visit, as long as there are no concurrent AEs associated with immunogenicity.

Subjects who test positive for teduglutide-specific antibodies at the end of Stage 2 will be allowed to enter Stage 3, as long as there are no concurrent AEs associated with immunogenicity. The presence of teduglutide-specific antibodies will continue to be monitored at every visit until the end of this study. If, at the final visit, the subject is still positive for teduglutide-specific antibodies, the subject will require follow-up blood draws as specified above. If any subject (previously negative for teduglutide antibodies) has specific anti-teduglutide antibodies at the final visit of this study, they will have follow-up blood draws for antibodies at Months 2, 3 and 6 post-study. These may be done at a local laboratory convenient to the subject, however all blood samples will be mailed to the central laboratory for analysis. If a subject's results are negative at 2 successive visits within this time, follow-up may be terminated. If at the end of 6 months the subject is still determined to have

teduglutide-specific antibodies, the PI and the sponsor will determine if additional follow-up may be required. During this follow-up, subjects will be evaluated for AEs or SAEs related to immunogenicity, which will be collected in the Pharmacovigilance database. Collection of AE and/or SAE information may be done via telephone contact.

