### **6.2.16.1 Colonoscopy/Sigmoidoscopy**

A colonoscopy/sigmoidoscopy of the remnant colon with polyp removal will be performed prior to teduglutide exposure (during stabilization) in subjects with any colon remnant including rectal stump evaluation. This will be repeated at Visit 10 in Stage 2 and at the end of teduglutide exposure in Stage 3. A colonoscopy is required at the beginning of the study, at the end of the main treatment period and at the end of the study to determine if any clinically significant changes have occurred. The date and result of colonoscopy are to be recorded in the CRF. If a subject had a normal colonoscopy within 6 months prior to screening, a baseline colonoscopy/sigmoidoscopy will not be required.

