#### **6.4 Schedule of Evaluations and Procedures**

All clinical study evaluations prior to treatment with teduglutide will be performed according to the Schedule of Evaluations and Procedures – Stage 1, [Table 6-1](#). All clinical study evaluations during the first 24 weeks of treatment will be performed according to the Schedule of Evaluations and Procedures – Stage 2, [Table 6-2](#). All clinical study evaluations during the extension will be performed according to the Schedule of Evaluations and Procedures – Stage 3, [Table 6-3](#).

Subjects who drop out of the study prior to the final visit should have all end-of-study procedures done.

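### Recording of new non-serious adverse events stops at the last dose, although the protocol's own definition of an adverse event includes later events caused by required procedures

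*Protocol*

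**What the plan says.** Section 6.2.1.1 lists what counts as an adverse event and includes "Pretreatment or post-treatment events that occur as a result of protocol-mandated procedures". It does not restrict this to serious events.

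Section 6.2.1.2 sets the recording period for adverse events in general: "Adverse events will be recorded from the signing of the ICF through the last dose of study drug". It also provides for contact after the last dose: "Adverse events that are not resolved at the end of study will be monitored with a telephone call by the investigator". That contact is made as necessary, for about 4 weeks.

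Section 6.2.2 gives serious events a longer period: "Any SAEs occurring from the signing of the ICF through 30 days after the last dose of study drug will be captured".

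On procedures near the end of treatment, Section 6.2.16.1 says of the colonoscopy/sigmoidoscopy: "This will be repeated at Visit 10 in Stage 2 and at the end of teduglutide exposure in Stage 3". Section 6.4 adds: "Subjects who drop out of the study prior to the final visit should have all end-of-study procedures done". Under the heading on antibodies in Section 6.2.4, subjects who are antibody-positive at the final visit have blood draws after the study at Months 2, 3 and 6. During that follow-up only immunogenicity-related events are collected, in the pharmacovigilance database.

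These definition and recording sentences are the same in all three protocol versions in the file whose Section 6 is shown.

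**The concern.** The definition and the recording rule do not fit together. A non-serious event that follows a required procedure after the last dose is an adverse event under one subsection, and the next subsection gives no instruction to record it. Two sites could read the pair differently and both claim compliance.

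Safety is the first objective named in Section 2, and at least 5 subjects are planned, so a single unrecorded event is a visible share of the safety record. The subjects most exposed are those who stop early, because their end-of-study procedures can be done after dosing has already ended.

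**Working it through.** No power, alpha or sample-size figure is involved, and the protocol states no figure to reproduce. The check sets the provisions side by side.

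**Capture after the last dose**

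| Type of event | Source | Days captured after last dose |
|---|---|---|
| New non-serious event | Section 6.2.1.2 | 0 |
| Serious event | Section 6.2.2 | 30 |

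Difference: 30 − 0 = 30 days. If exactly 5 subjects were dosed (the stated minimum) and none stayed on the drug afterwards, this would be 5 × 30 = 150 subject-days. Both conditions are assumptions. The figure only illustrates the scale and does not estimate lost events.

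**Can required procedures fall at or after the last dose?**

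1. The Stage 3 colonoscopy/sigmoidoscopy is set "at the end of teduglutide exposure in Stage 3". Table 6-3 places it in the final or early-termination column, and no scheduled visit follows.
2. Subjects who stop early are to have the end-of-study procedures (Sections 4.4 and 6.4). Nothing requires these to be done before the last dose.
3. Table 6-3 marks a possible interim safety visit in the final column. Its footnote d puts such a visit 5 to 7 days after a visit at which PN/I.V. was reduced, with laboratory measurements.
4. For antibody-positive subjects: "they will have follow-up blood draws for antibodies at Months 2, 3 and 6 post-study". At 30 days per month, that is about 60, 90 and 180 days.

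**Does any other provision record a new non-serious event there?**

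1. The 30-day period in Section 6.2.2 applies only to serious events.
2. The telephone contact of about 4 weeks follows events already open at the end of the study. It does not ask for new ones.
3. The collection during antibody follow-up is limited to events related to immunogenicity.
4. Tables 6-2 and 6-3 have an adverse-event row at the final or early-termination visit. This catches what is noticed at that visit, but not what develops afterwards from a procedure done there. If the visit comes after the last dose, the row itself goes beyond the period in Section 6.2.1.2.

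A new non-serious procedure event that arises after the final or early-termination visit is therefore left without a recording route.

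**The case against.** The strongest reply is that a definition and a recording period do different jobs, and that a shorter period for non-serious events is a legitimate design choice. The post-treatment clause is not empty under the present periods: serious events are a subset of adverse events and are captured for 30 days, and antibody follow-up collects some events later still. This stands in part. It makes the gap small, but it does not supply a route for the non-serious remainder that the definition includes without qualification.

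The colonoscopy argument also has limits. For subjects who continue, the Visit 10 examination falls within ongoing dosing, so its after-effects are recorded. The protocol ties the Stage 3 examination to the end of exposure without saying that it follows the last dose. Both points stand.

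A reader might infer more than the document supports:

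- *That every subject has about 30 unobserved days off drug.* Stage 3 may run until the product is commercially available, so subjects who move directly to commercial drug may have no drug-free period.
- *That fluid-balance symptoms after stopping are being missed.* The protocol gives no frequency for them.
- *That the adverse-event tables will be wrong.* The system organ class and preferred term tables in Section 8.3.1 are of treatment-emergent events. The protocol shown does not define that period, which is commonly left to the analysis plan. Post-treatment events might not enter those tables even if recorded.

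Finally, the newest protocol version in the file stops within its Summary, before Section 6.2.1. Other passages did change between versions, so the sentence may have changed too.

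**Conclusion.** The inconsistency is real in every version whose Section 6 can be read. Followed as written, the protocol defines certain post-treatment procedure events as adverse events and then provides no means of recording them when they are new, non-serious and arise after the final or early-termination visit.

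The size is modest: 0 days of capture against 30 for serious events, in subjects who actually stop the drug or have a required procedure at or after the last dose. No event rate is given, so the number of events lost cannot be estimated. No efficacy result is affected. This is a worthwhile correction to safety capture in a very small trial, not a flaw that threatens its conclusions. It rests on the assumption that the sentence survives in the version that is cut off.

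**What to change.** The sponsor should first confirm that the sentence in Section 6.2.1.2 still stands in the newest version. If it does:

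1. Record all adverse events, serious or not, from consent through 30 days after the last dose, to match Section 6.2.2.
2. Make the telephone contact already foreseen routine for every subject leaving the study, at about day 30. A call at exactly 4 weeks (28 days) would fall 2 days short of the period.
3. Add a clause that events resulting from procedures required later, namely the antibody draws at Months 2, 3 and 6, are also recorded. A 30-day period alone would miss them.
4. Flag events with onset after the last dose and tabulate them separately, so that on-treatment summaries are unchanged.

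The cost is a short amendment to one section and about one call per subject. The downside is that a few late, unrelated events will appear in the listing.
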